9.9 Pre-planned Subgroup Analysis

It is planned to evaluate the primary and secondary endpoints on multiple subsets of study subjects based upon variables such as geography, demographics, investigator experience, lesion and procedure characteristics, and other variables as deemed appropriate. The subgroup analyses are exploratory in nature, for the purpose of evaluating the safety and effectiveness performance of the study device under various clinical conditions.

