6.0 Introduction**6.1 Background/Justification of Investigation**

Rapid and precise diagnosis of suspicious lesions is crucial to determine the optimal treatment for lung disease. Diagnosis of peripheral lung lesions, which comprise 25-30% of all lung lesions, is particularly challenging (3, 4).

Technologies that allow for earlier diagnosis and treatment of malignant lung disease are crucial for improving survival rates. According to the American Cancer Society's 2014 estimates, the survival rate for distant (metastasized) lung cancer is 4%, compared to 26% for regional cancer and 54% for localized cancer (5).

Electromagnetic navigation bronchoscopy (ENB)TM is an image-guided approach that uses 3D-reconstructed computed tomography (CT)-scan and sensor location technology to guide a steerable endoscopic probe to peripheral lung lesions that may be beyond the reach of conventional bronchoscopes (5-7).

Over 24 original research articles have been published describing outcomes following ENB to aid in the diagnosis of peripheral lung lesions and mediastinal lymph nodes (3, 6-28). Diagnostic yield aided by ENB in these studies has ranged from 59.0% to 94.0%, with rates generally higher in more recent analyses (3, 6, 9, 10, 15, 17, 18, 20, 23-25).

ENB is also associated with a more favorable safety profile than alternative techniques; in a meta-analysis of 15 studies representing data from over 1000 lung nodules, the pneumothorax

rate after ENB was only 3.1% (29). In comparison, in a meta-analysis of 19 studies, the median pneumothorax incidence rate following CT-guided transthoracic biopsy was 25% (range 4% to 60%) (30).

Despite these promising results, outcomes following ENB are widely varied and most evidence to date is based on single-center analyses (21 of the 24 published studies) with only 3 studies enrolling greater than 100 subjects (see Table 1). The impact of user/center experience, patient risk factors, and lesion characteristics remains largely unexplored in a large multi-center study. In addition, further information is needed about the use of ENB to place dye markers to allow biopsy and surgery in the same procedure, the use of ENB to place fiducials to enable radiation therapy, the adequacy of cells and tissue captured using ENB for genomic testing, the impact of ENB on stage of diagnosis, and the cost effectiveness of ENB.

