8.6.4.1 Baseline

The following assessments will be performed within 30 days prior to the scheduled ENB procedure:

- Signed informed consent
- Eligibility criteria
- Demographics
- Medical history (including smoking history, lung history, anticoagulant and anti-platelet therapy medications, and risk factors)
- Quality of life questionnaire assessment utilizing EQ-5D

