9.1 General

All statistical analyses will be performed using Statistical Analysis System (SAS) for Windows (version 9.2 or higher, SAS Institute Inc. Cary, NC) or other widely accepted statistical or graphical software. In general, data for all study subjects combined will be presented. Individual data will be presented in subject listings.

Descriptive statistics will be used to present the data and to summarize the results. Discrete variables will be presented using frequency distributions and cross tabulations. Continuous variables will be summarized by presenting the number of observations (N), mean, standard deviation, median, minimum, and maximum values.

In general, data analysis will be conducted on all subjects who are enrolled in the trial and undergo an ENB procedure utilizing the superDimension™ navigation system. Analyses will be conducted on multiple subsets of study subjects based upon variables such as geography, demographics, investigator experience, lesion and procedure characteristics, and other variables as deemed appropriate. Results from interim and final analyses will be presented and/or published as defined in the Publication Plan.

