9.5 Endpoint Analysis

For the primary and secondary endpoints, descriptive statistics will be provided. The endpoints will be summarized using frequency measures such as count and percentage. For the primary endpoint, a 2-sided 95% exact binomial confidence interval will also be provided.

Adverse events for all enrolled subjects will be collected and reported for each follow-up visit. For adverse event reporting, which includes the primary and secondary endpoints, the primary analysis will be based on subject counts (e.g., the number and percentage of subjects with event among the total number of Subjects). The data will be presented in the format of p% (x/N) [e], with p and x being the percentage and number of subjects with events, respectively, N being the sample size of the analysis population, and e being the total number of events occurred in the x subjects. For example, the data of 2% (20/1000) [38] indicates that a total of 38 events occurred in 20 subjects out of a total of 1000 subjects (2%).

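### The protocol plans only unadjusted subsets to study experience, patient and lesion effects; one pre-specified adjusted model for diagnostic yield should be added

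*Combined protocol and SAP*

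**What the plan says.** Section 6.1 states: "The impact of user/center experience, patient risk factors, and lesion characteristics remains largely unexplored in a large multi-center study". The same paragraph lists other gaps: dye marking, fiducial placement, tissue adequacy for genomic testing, stage at diagnosis and cost effectiveness.

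Three places in the protocol address how outcomes vary with these factors.

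- Section 9.9: "It is planned to evaluate the primary and secondary endpoints on multiple subsets of study subjects based upon variables such as geography", followed by demographics, investigator experience, lesion and procedure characteristics, and an open-ended remainder. It adds: "The subgroup analyses are exploratory in nature".
- Section 9.1 repeats the plan: "Analyses will be conducted on multiple subsets of study subjects based upon variables such as geography, demographics, investigator experience, lesion and procedure characteristics". It also says: "Discrete variables will be presented using frequency distributions and cross tabulations".
- Section 9.2 has roll-in subjects (at most five per investigator) analysed apart from the rest, in order to detect outcome differences that go with investigator experience.

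Section 9.5 sets the method: "For the primary and secondary endpoints, descriptive statistics will be provided". It adds one inferential element: "For the primary endpoint, a 2-sided 95% exact binomial confidence interval will also be provided".

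On data, Section 8.6.4.1 collects "Medical history (including smoking history, lung history, anticoagulant and anti-platelet therapy medications, and risk factors". Section 8.6.4.2 and Table 2 add procedural information and lesion characteristics. Section 9.7 shows that roll-in status is flagged at enrolment. Section 9.0 refers to a separate SAP for methods; its text is not in the document reviewed here.

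**The concern.** Lesions are not allocated to operators at random. If experienced operators, or operators in one region, take on more of the difficult lesions, a yield table by experience or geography mixes the operator effect with the lesion effect. The roll-in comparison in Section 9.2 has the same weakness, although its stated purpose is to detect differences due to experience. Subjects are also grouped within sites, with up to 75 at each (Section 9.3), and the text makes no allowance for that.

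At stake is the interpretation of a published subset result. The study could report that experience or geography matters when only case mix differs, or that it does not matter when case mix has masked a real effect. A larger sample does not cure this. The overall incidence of the primary endpoint is not affected.

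**Working it through.** **Figures in the plan that can be checked.** Section 10.1 gives 32 pneumothoraces in 1,033 nodules, 17 of them needing a chest tube. 32/1,033 = 3.10% and 17/1,033 = 1.65%, which agree with the stated 3.1% and 1.6%. The ceiling of 2,500 cannot be reproduced, because Section 9.3 says no formal estimate was made.

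**How a real effect can be hidden.** All inputs here are assumptions: yield of 80% in large and 65% in small lesions for less experienced operators, and a true odds ratio for experience of 1.5.

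- Large lesions: odds 0.80/0.20 = 4.000; × 1.5 = 6.000; yield 6.000/7.000 = 85.7%.
- Small lesions: odds 0.65/0.35 = 1.857; × 1.5 = 2.786; yield 2.786/3.786 = 73.6%.
- Difference standardised to a 50/50 lesion mix: (5.7 + 8.6)/2 = 7.1 points.

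| Small lesions: experienced / others | Experienced | Others | Crude difference |
|---|---|---|---|
| 50% / 50% | 79.6% | 72.5% | 7.1 points |
| 60% / 40% | 0.4 × 85.7 + 0.6 × 73.6 = 78.4% | 0.6 × 80 + 0.4 × 65 = 74.0% | 4.4 points |
| 70% / 30% | 0.3 × 85.7 + 0.7 × 73.6 = 77.2% | 0.7 × 80 + 0.3 × 65 = 75.5% | 1.7 points |

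The loss is 38% in the second row and 76% in the third. It is nil when the mix is balanced.

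**How a false effect can arise.** Assume that experience has no effect, and that yield is 80% in easy and 60% in hard lesions.

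- Hard lesions 70% against 30%: experienced 0.3 × 80 + 0.7 × 60 = 66%; others 0.7 × 80 + 0.3 × 60 = 74%. This is a false 8-point deficit.
- Hard lesions 60% against 40%: 68% against 72%, a false 4-point deficit.
- A milder contrast borrows the two period yields in Section 6.2.2, 78.5% and 69.0%, as the easy and hard yields (assumption). The gap is 9.5 points, so the false difference is 9.5 × 0.2 = 1.9 points at 60/40 and 9.5 × 0.4 = 3.8 points at 70/30.

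In 1,000 simulated studies of 2,500 subjects (80%/60% yields, 70/30 mix, no site effects), the crude odds ratio averaged 0.68 and was significant at the two-sided 5% level in 99%. Adjusted for lesion type, it averaged 1.00 and was significant in 4.8%. The protocol plans no such test; significance serves here only as a yardstick.

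**How much information a model would have.** The allowance of 10 or 20 events per model term is an assumed rule of thumb.

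| Endpoint | Events at the 2,500 ceiling | Terms at 10 / 20 events each |
|---|---|---|
| Non-diagnostic at 73.6% yield (Section 6.2.2) | 2,500 × 0.264 = 660 | 66 / 33 |
| Non-diagnostic at 59.0% and 94.0% yield (range in Section 6.1) | 1,025 and 150 | 102 / 51 and 15 / 7 |
| Grade 2+ pneumothorax, 17/1,033 as stand-in | about 41 | 4 / 2 |
| Any pneumothorax, 32/1,033 | about 77 | 7 / 3 |

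All these counts are maxima for their rates: 2,500 is a ceiling and includes roll-ins. The non-diagnostic counts are reduced further because yield applies only to lesion procedures (Section 8.2.2). Events per term is also not the whole constraint. Region and prior experience vary between sites and investigators, so their precision depends mainly on how many of those there are: at most 75 sites, and an unstated number of investigators.

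**The case against.** The strongest reply is that this is a descriptive registry. Section 8.1 aims to evaluate outcomes, no hypothesis is tested, and Section 9.9 presents the subsets as exploratory views of performance under different clinical conditions. A crude subset rate answers that descriptive question, and no section promises an independent effect of experience. This stands as a limit on severity. It does not dispose of the point, because Section 9.2 explicitly looks for differences related to experience, and an exploratory label lowers the strength of a claim without removing confounding.

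A reader might infer more than the documents support in four ways.

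- *That subsets are the only method anywhere.* Section 9.0 defers to a separate SAP that may contain a model. Cross tabulations in Section 9.1 could also stratify experience by lesion size, although none is pre-specified.
- *That these factors are the study's one evidence gap.* Section 6.1 lists several others beside them.
- *That every covariate is already recorded.* Table 2 has no item for investigator experience. The text shows only the roll-in flag and qualification records in the study files. Lesion characteristics are not itemised, so size and location need confirming.
- *That most of a real effect will be lost.* The 38% and 76% follow from the chosen lesion mixes, and no section reports how mix varies with experience.

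**Conclusion.** The point holds as a worthwhile improvement. The protocol names these influences among its open questions and looks for experience effects, but the text available plans only unadjusted descriptive summaries, which cannot separate correlated factors.

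The size of the bias is unknown. Under the assumed inputs it ranges from none, with a balanced lesion mix, to a false 8-point deficit or the loss of about three quarters of a 7.1-point effect.

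The case for a model is good for diagnostic yield, within the upper bound of about 660 non-diagnostic cases and the limit set by the number of sites and investigators. It is weak for the primary endpoint. About 41 events assumes that chest-tube drainage stands in for Grade 2 or higher, and it would be inferred wrongly from the yield figures that all the listed factors could be separated there too.

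**What to change.** In Section 9.9, or in the separate SAP if it does not already do so, pre-specify one logistic model for diagnostic yield among lesion-biopsy procedures.

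- *Population:* the overall cohort, so that roll-in status can enter as a term. The separate roll-in summary stays.
- *Clustering:* allow for site. Add an investigator level only if sites have several investigators; otherwise the two levels cannot be separated.
- *Terms:* investigator experience (roll-in status or case sequence within investigator; prior volume only if confirmed as recorded), lesion size and location as recorded, smoking and lung history, and region. Yield is counted per patient (Section 5.2), so state which lesion supplies size and location when several are biopsied.
- *Reporting:* adjusted results next to the crude subsets. State that about 660 non-diagnostic cases is a maximum, and that precision for experience and region depends mainly on the number of sites and investigators.
- *Grade 2 or higher pneumothorax:* at most a small penalised model, or leave the summary descriptive.

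The cost is SAP wording, modest programming and a check of which variables are recorded. The downside is some dependence on the model, which showing both sets of results keeps visible. No extra subjects or visits are needed.

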10.0 Risk/Benefit Analysis

All devices utilized in this study are commercially available. There are no anticipated risks related to inclusion of subjects in this clinical study above and beyond anticipated risks related to any ENB procedure. All records identifying the subject will be kept confidential and, to the extent permitted by the applicable laws and/or regulations, will not be made publicly available. Subject names will be kept confidential. Outside of the normal procedure, the study may or may not be of benefit to the study subject. The data collected from this study will help to establish new information on the ENB procedure and the diagnosis and treatment of lung lesions.

10.1 Risks of ENB

Rex et al. performed a systematic review and a meta-analysis of ENB for the evaluation of peripheral lung lesions. A total of 15 studies, representing data from 1,033 lung nodules, were included. A total of 32 pneumothoraces were reported (3.1%), of which 17 (1.6%) required chest tube drainage. Nine cases of minor or moderate bleeding were reported, none requiring treatment or intervention. Other reported complications were 1 self-limited hematoma event and 1 episode of hypercapnic respiratory failure attributed to sedation (29).

Table 1 in Section 6.2.2 above lists pneumothorax rates in ENB studies published in the Rex meta-analysis, with the addition of more recently published ENB studies (24 studies in total). The weighted mean pneumothorax rate specifically for ENB procedures based on the data provided in Table 1 is 3% (range 0% to 13%).

11.0 Adverse Events & Complications

Adverse events will be collected after the ENB index procedure has been initiated (defined as introduction of the Locatable Guide into the subject). During the course of the study, the following AEs will be collected and reported on the eCRF:

- All AEs related to the superDimension™ navigation system, associated tools, or ENB procedure (both index and any subsequent repeat ENB procedure)
- All deaths
- All pneumothoraxes
- All bronchopulmonary hemorrhages
- All respiratory failures

11.1 Adverse Event (AE)

An AE is any untoward medical occurrence, unintended disease or injury, or untoward clinical signs (including abnormal laboratory findings) in subjects, users or other persons, whether or not related to the investigational medical device.

NOTE: Documented pre-existing conditions are not considered to be reportable AEs unless there is a change in the nature or severity of the condition.

11.2 Serious Adverse Event (SAE)

A serious AE (SAE) is an AE that has

- a) led to death,
- b) led to serious deterioration in the health of the subject, that either resulted in
 - 1) a life-threatening illness or injury, or
 - 2) a permanent impairment of a body structure or a body function, or
 - 3) in-patient or prolonged hospitalization, or
 - 4) medical or surgical intervention to prevent life-threatening illness or injury or permanent impairment to a body structure or a body function,
- c) led to fetal distress, fetal death or a congenital abnormality or birth defect

NOTE: Planned hospitalization for a pre-existing condition, or a procedure required by the study, without serious deterioration in health, is not considered a serious AE.

11.3 Unanticipated Adverse Device Effect (UADE)

An unanticipated adverse device effect (UADE) is an adverse event related to the study device which by its nature, incidence, severity or outcome has not been previously identified in product risk analysis.

11.4 Adverse Event Relationship Classification

Relationship to study product administration will be determined as follows:

- *Not related*: No relationship between the AE and the administration of study treatment and a known relationship to other etiologies such as concomitant medications, surgical procedure or subject's clinical state.
- *Related*: An AE that follows a plausible temporal sequence from administration of the study treatment and follows a known response pattern to the study treatment. The reaction cannot be reasonably explained by the known characteristics of the subject's clinical state or other modes of therapy administered to the subject.
- *Impossible to Determine*: Given the information available, sequence and timing of events, it is impossible to determine the relationship of the AE with the study treatment.

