11.7 Adverse Event Reporting

Please refer to Table 3 for a list of the minimum AE reporting requirements for investigators. If local regulations or IRB/EC require faster reporting, then the investigator will adhere to those requirements.

Table 3: Investigator AE Reporting Requirements

Type	Report to	Reporting Timeframe (from time of learning of the event)
Adverse Event	Sponsor	Recommended within 10 working days
	IRB/EC	Per IRB/EC reporting requirements
Serious Adverse Event	Sponsor	Recommended within 24 hours, required within 10 working days
	IRB/EC	Per IRB/EC reporting requirements
Unanticipated Adverse Device Effect	Sponsor	Recommended within 24 hours, required within 10 working days
	IRB	Required within 10 working days
	EC	Per EC reporting requirements

Events will be reviewed by Medtronic or designee to determine any reporting obligations to FDA or Competent Authorities as well IRB/EC. Reporting will occur within the timelines per local regulations and requirements.

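### Requiring a known response pattern for a Related rating (11.4) leaves a harm of a truly new kind with no clear route to UADE status (11.3) or onto the eCRF (11.0)

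*Combined protocol and SAP*

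**What the plan says.** Section 11.4 gives three relationship categories.

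- **Related** needs an event that "follows a plausible temporal sequence from administration of the study treatment and follows a known response pattern to the study treatment". A further sentence adds: "The reaction cannot be reasonably explained by the known characteristics of the subject's clinical state or other modes of therapy administered to the subject".
- **Not related** needs "No relationship between the AE and the administration of study treatment and a known relationship to other etiologies".
- **Impossible to Determine** applies where, on the information available, "it is impossible to determine the relationship of the AE with the study treatment".

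Section 11.3 defines a UADE as an adverse event "related to the study device which by its nature, incidence, severity or outcome has not been previously identified in product risk analysis".

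Table 3 in section 11.7 sets the investigator's deadlines. For both SAEs and UADEs the limit to the sponsor is "Recommended within 24 hours, required within 10 working days". For an ordinary adverse event, 10 working days is only recommended. A fixed limit to the IRB, 10 working days, appears in the UADE row alone; the other rows defer to IRB/EC requirements.

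Section 11.0 lists what is collected on the eCRF: adverse events related to the "navigation system, associated tools, or ENB procedure (both index and any subsequent repeat ENB procedure"), plus all deaths, pneumothoraxes, bronchopulmonary hemorrhages and respiratory failures, whatever their relationship.

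**The concern.** The conditions for Related are joined by 'and', so a known response pattern is necessary. A harm of a kind not seen before has no such pattern. Yet 11.3 expects that some device-related events will be unanticipated by their very nature. The two definitions pull against each other for exactly the events that the nature route most obviously serves.

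At stake is safety capture outside the named events. A post-market study of up to 2,500 subjects is a natural place to meet an unexpected device harm. If investigators apply 11.4 as written, such a harm is steered away from Related. It may then miss UADE assessment, and because 11.0 collects unnamed events only when they are related, it may not be recorded at all. A final statement that few or no UADEs occurred would then partly reflect the definition.

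**Working it through.** No sample size, error rate or event rate enters this point, and the plan states no figure to reproduce. The check sets 11.0, 11.2, 11.3, 11.4 and Table 3 side by side.

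**Step 1: classify a new harm under 11.4.** Take an event with plausible timing, no other reasonable explanation, and no known response pattern.

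- Related: timing is met, absence of another explanation is met, known pattern is not met. It fails.
- Not related: this needs a known relationship to another cause. There is none. It fails.
- Impossible to Determine: the only category left, although the obstacle is the wording of Related rather than a lack of information.

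**Step 2: carry the result into 11.3.** A UADE must first be related to the device. It must then be unanticipated by nature, incidence, severity or outcome, judged against the product risk analysis.

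| Case | Related under 11.4? | UADE under 11.3? |
|---|---|---|
| (a) New kind of harm, no known pattern | No | No, if the 11.4 rating governs the word 'related' in 11.3 |
| (b) Known kind of harm, unanticipated incidence, severity or outcome | Possible | Possible |
| (c) Pattern known, but absent from the product risk analysis | Possible | Possible, including by nature |

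The conflict is confined to case (a).

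**Step 3: read the consequence for case (a) from Table 3 and 11.0.**

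| | With UADE status | Rated Impossible to Determine |
|---|---|---|
| Serious: limit to sponsor | 24 hours recommended, 10 working days required | The same, through the SAE row; the SAE definition in 11.2 has no relatedness condition |
| Serious: limit to IRB | 10 working days required | Per IRB/EC requirements |
| Non-serious: limit to sponsor | 24 hours recommended, 10 working days required | 10 working days, recommended only |
| Non-serious: limit to IRB | 10 working days required | Per IRB/EC requirements |
| On the 11.0 collection list | Yes, as a related event | Only if a death, pneumothorax, bronchopulmonary hemorrhage or respiratory failure |

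The last row also shows that 11.0 and Table 3 do not agree. Table 3 sets a deadline for every SAE, whereas 11.0 does not list an SAE that is neither rated related nor one of the named events.

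**Step 4: primary endpoint.** Pneumothorax is a known response to the procedure, and all pneumothoraxes are collected whatever their rating. The known-pattern condition therefore does not touch the primary endpoint.

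**The case against.** Four things can fairly be said against the point.

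**The sections are not formally linked.** 11.3 does not cite 11.4. It speaks of an event related to the study device, 11.4 of study product administration and study treatment, and 11.0 of the system, tools or ENB procedure. A reader might infer that a new kind of harm can never be a UADE, or that the count of UADEs by nature must be zero. The documents do not support that: no text says the 11.4 rating decides UADE status. What remains is that 11.4 is the only definition of relatedness in the protocol and directly follows 11.3, so an investigator has no other standard to apply.

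**The benchmarks differ.** A known response pattern is not the same thing as prior identification in the product risk analysis. Cases (b) and (c) stay open, so the nature route is narrowed rather than closed. This stands in full.

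**Serious events are still reported.** A reader might infer that a new harm drops out of expedited reporting. For a serious event it does not, because the SAE row carries the same sponsor limit as the UADE row. Section 11.7 adds that the sponsor or its designee reviews events for onward reporting to authorities and IRB/ECs. This also stands, with one limit: the review can act only on events that reach the sponsor, and 11.0 does not list this one. The medical monitor in 12.1 does not fill the gap, since that role covers pre-specified events supporting the endpoints.

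**UADE counts are not an endpoint**, and the main known harms are collected regardless of relationship. True; this limits the importance of the point but does not remove the contradiction.

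**Conclusion.** The concern holds in a narrow form. Read literally, 11.4 sends a device or procedure harm of a truly new kind to Impossible to Determine. That conflicts with the nature route to UADE status in 11.3, and nothing says how the category is treated for UADE assessment or for collection. The certain loss, if the event is then not treated as a UADE, is the fixed 10-working-day IRB limit. For a non-serious event the sponsor limit also weakens from required to recommended. The most important loss is a possible one: an event outside the named types may never be recorded.

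This rests on two assumptions: that investigators use 11.4 to decide what counts as related in 11.3 and 11.0, and that they follow its wording literally.

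The size cannot be given as a number. One could calculate the chance of seeing a rare harm among 2,500 subjects: at an assumed 1 in 1,000 it is 1 − (1 − 0.001)^2500 = 0.918, and at an assumed 1 in 2,000 it is 1 − (1 − 0.0005)^2500 = 0.714. Those figures give only the chance that a harm of assumed incidence occurs at the maximum enrollment. They do not say how often it would be misclassified or missed, and should not be read as the size of the defect.

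**What to change.** Reconcile 11.0, 11.3, 11.4 and Table 3.

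- **11.4:** make a known response pattern supportive, not required. For example: an event is Related if its timing is plausible and neither the subject's condition nor other therapy reasonably explains it; a known response pattern supports this rating but is not needed for it.
- **11.0:** add to the collection list events whose relationship to the system, tools or ENB procedure is Impossible to Determine, and state that they go to the sponsor for UADE assessment under 11.3. Without this, a change to 11.4 alone would leave the list out of step.
- **11.3:** say whether 'related' means the 11.4 rating, and use one description of the object (device, tools, procedure) in all three sections.
- **Table 3:** say which row applies while UADE assessment is pending, and whether the SAE row covers every SAE or only those on the 11.0 list.

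The cost is a few sentences, revised eCRF guidance, and the approvals that 13.2 requires for any protocol change. More events will be recorded and reviewed. The documents give no basis for estimating how many, and the number may not be trivial, because subjects with lung lesions are monitored for adverse events over 24 months. The reported rate of related adverse events may also rise slightly.
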